RESEARCH PROPOSAL

Version 1

Date: January 8, 2015

1. General Information

Title:

A randomized double blinded study comparing the live birth rate of IVF treatment following brief incubation of oocytes and spermatozoa versus standard incubation

Principal Investigator:

[name] [name]

Clinical associate Professor, Center of Assisted Reproduction, Shanghai first Maternity and Infant health hospital, Tong Ji University

Co-Investigators:

[name] [name], [name], [name] [name], [name] [name], [name] [name],

Shanghai first Maternity and Infant health hospital, Tong Ji University

[name] [name]

Department of Obstetrics and Gynaecology, The University of Hong Kong

Correspondence to:

[name] [name], Center of Assisted Reproduction, Shanghai first Maternity and Infant health hospital, Tong Ji University

[name]

[contact]

Email : [contact]

2. Background

In vitro fertilization (IVF) treatment is now commonly used to treat infertile couples. During IVF treatment, oocytes and sperm are routinely incubated overnight and this may lead to suboptimal culture conditions because of increased reactive oxygen species (ROS) produced by sperm in the standard incubation [1]. High levels of ROS can adversely affect the quality of the embryos, result in hardening of the zona pellucida and impair the implantation capacity of embryos [2-4]. Studies shows successful fertilization of an oocyte occurs 20mins after the gametes are put together [5]. Sperm can penetrate through the cumulus cells within 15min, and 80% of oocytes can be fertilized when they are exposed to a large number of spermatozoa within 1hr

[1]. As an attempt to avoid possible detrimental effects on the oocytes from long exposure to sperm, the brief incubation insemination protocol was developed. It implies that prolonged incubation of oocytes and sperm may not be necessary and may even be harmful. Some reports suggest that a sperm-oocyte exposure time of 1–6 h improves IVF outcomes [1,2,6,7]. However, other studies report no such advantage with a short insemination time [8,9,10].

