6.2 Insemination Procedures

All semen samples were prepared by the conventional swim-up procedure. At 2hr after oocyte retrieval, each matured oocyte will be inseminated with approximately 50,000–100,000 motile spermatozoa.

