6.3 Assignment and masking

On the day of OPU, patients will be randomized after oocyte pick up by a laboratory technician according to a computer generated randomization list in sealed envelopes into the brief incubation group or the standard incubation group. Until the completion of the whole study, both the patients and the clinicians were blinded to the group assigned.

Control arm

Women who allocated to the standard incubation group, all oocytes will be exposed to spermatozoa for 20 hours, and checked for fertilization on day 1 (20 hours) after denuding

Intervention arm

For those allocated to the brief incubation group, all oocytes will be exposed to spermatozoa for 2 hours and gently washed through two organ dishes containing 1.5 ml of equilibrated medium, and then transferred to the corresponding microdroplet of equilibrated fresh medium. Surrounding cumulus cell will be retained, not removed from the oocytes.

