6.4 Fertilization and Embryo Evaluation

Both groups of oocytes will be decoronated and checked for the presence of two pronuclei and two polar bodies to confirm fertilization. All other

outcomes (i.e., no fertilization, one pronucleus, polyspermy, degeneration) will be recorded.

Embryo morphology will be assessed every day of culture. Embryos will be scored according to the following criteria. Briefly, embryos are classified as: grade A, no cellular fragmentation; grade B, <20% fragmentation; grade C, 20% to 50% fragmentation; and grade D, >50% fragmentation. The number of blastomeres per embryo was also recorded. Grade A and B embryos constituted the “good quality embryo”.

The transfer is performed by the team clinician with a maximum of 2 embryos being replaced according to the standard protocol under transabdominal ultrasound guidance. Luteal phase support is given at the discretion of the physician.

6.5 Follow up strategy:

A pregnancy test will be carried out 2 weeks after embryo transfer in both arms. All women who have a positive pregnancy test 2 weeks after a fresh embryo transfer will undergo a transvaginal ultrasound scan after a further 2 weeks to identify the presence of a gestation sac with a fetal heart signifying an ongoing pregnancy.

Data on all pregnancy outcomes including early pregnancy losses such as miscarriage or ectopic pregnancy will be collected.

In order to achieve consistency with respect to the collection of outcome, standardised case report forms (CRF) will be completed for each woman at each centre. These CRFs will include details on treatment received, pregnancy outcomes, complications in pregnancy, mode of delivery and birth outcomes.

7. Study outcomes

Primary outcome is the live birth rate.

Secondary outcomes:

- Miscarriage rate
- Clinical pregnancy rates
- Normal fertilization rate
- polyspermy rate(≥ 3 PN)
- Cleavage rate
- High quality embryo formation rate
- Implantation rate

8. Statistics

8.1 Analysis plan:

Demographic factors and clinical characteristics collected as part of baseline data collection will be summarised with counts (percentages) for categorical variables, mean (standard deviation [SD]) for normally distributed continuous variables, or median (interquartile [IQR] or entire range) for other continuous variables.

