Outcomes for participants will be analysed in the groups to which they are assigned regardless of deviation from the protocol or treatment received (intention-to-treat). Comparative statistical analysis will entail calculating the relative risk (RR) (95% CI) for the primary outcome (99% CIs for all dichotomous secondary outcomes), the mean difference (99% CI) for normally distributed continuous secondary outcomes, or the median difference (99% CI) for skewed continuous variables.

All analyses will adjust for the minimisation factors to account for the correlation between treatment groups introduced by balancing the randomisation (which forces outcomes between treatment arms to be similar apart from any treatment effect).

Adjusted risk ratios will be estimated using a log binomial regression model, or using a log Poisson regression model with a robust variance estimator if the binomial model fails to converge. Linear regression will be used for normally distributed outcomes and quantile regression for skewed continuous variables.

Pre-specified subgroup analyses will include (i) Natural versus hormone replacement frozen replacement cycles, and (ii) Cleavage versus blastocyst stage transfer.

9. Sample size estimation:

The average live birth rate in our center from 2010-2012 was 30% per transfer. According to the recent meta-analysis[11], briefincubation of gametes was associated with significantly higher rates of ongoing pregnancy (RR: 1.73, 95%CI: 1.27–2.33) than standard insemination.

Assuming live birth in the brief incubation group increase from 30% to 50% (increase by 70%); with 90% power and a two-sided 5% level of statistical significance, we will need to recruit 124 women in each arm. To account for 10% loss to follow up, we will recruit 140 subjects in each group or 280 subjects for the whole study.

10. Assessment of safety

Results from a recent meta-analysis [11,12] showed the rates of normal fertilization, good quality embryos and polyspermy were not significantly different with short time incubation of gametes compared with standard insemination. Thus, there should be no major safety concern in this study.

11. Direct access to source data / documents:

Trial-related monitoring, audits, IRB review and regulatory inspections are allowed.

12. Quality control and quality assurance

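### Both pre-specified subgroups are defined by events after randomisation, and the frozen-cycle subgroup has no population described in the protocol

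*Protocol*

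**What the plan says.** Section 8.1 names two subgroup analyses and no others: "Pre-specified subgroup analyses will include (i) Natural versus hormone replacement frozen replacement cycles, and (ii) Cleavage versus blastocyst stage transfer". The same section commits to analysing women in their assigned groups whatever treatment they received.

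The timing is set out in section 6:

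- Allocation (6.3): "On the day of OPU, patients will be randomized after oocyte pick up by a laboratory technician".
- Insemination (6.2): "At 2hr after oocyte retrieval, each matured oocyte will be inseminated with approximately 50,000–100,000 motile spermatozoa".
- Fertilisation check, daily embryo grading and transfer (6.4) come later. On transfer the section says: "The transfer is performed by the team clinician with a maximum of 2 embryos being replaced according to the standard protocol". It gives no rule for choosing cleavage or blastocyst stage, and does not mention freezing.
- Follow-up (6.5): "All women who have a positive pregnancy test 2 weeks after a fresh embryo transfer will undergo a transvaginal ultrasound scan".

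Section 2 gives the rationale for shorter exposure to sperm: "High levels of ROS can adversely affect the quality of the embryos". Section 7 lists "High quality embryo formation rate" among the secondary outcomes, together with the normal fertilisation and cleavage rates.

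**The concern.** A subgroup comparison keeps the protection of randomisation only if a woman's subgroup cannot be altered by her allocation. Variables fixed before the envelope is opened meet that condition. Stage at transfer and type of frozen cycle are seen only after the allocated incubation has taken place, so they carry no such guarantee.

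Transfer stage is the more exposed of the two. It plausibly depends on how many embryos develop and how well, and that is the path by which brief incubation is expected to work. If allocation moves some women from cleavage to blastocyst transfer, the blastocyst women in the two arms are no longer alike in prognosis, and neither are the cleavage women. Both subgroup risk ratios can then differ from 1 although no woman's chance of live birth has changed.

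Two further problems follow from the wording. Women who have no transfer (or, for the first subgroup, no frozen transfer) fall in neither level and drop out for a reason that allocation may influence, which does not fit the intention-to-treat commitment. And the frozen-cycle subgroup refers to a form of treatment that the protocol does not describe, so its population is undefined.

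At stake is the credibility of the only subgroup results the protocol labels as pre-specified.

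**Working it through.** **Order of events.** Oocyte pick-up, randomisation (6.3), insemination 2 hours after retrieval (6.2), exposure for 2 or 20 hours (6.3), fertilisation check and daily grading (6.4), transfer (6.4). Transfer stage is settled at or shortly before the last step. A frozen replacement cycle needs embryos produced by the earlier steps. Both subgroup variables therefore follow allocation.

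**Where frozen cycles appear.** Only in the subgroup sentence of 8.1. Freezing, preparation for a frozen cycle, follow-up after one, and whether a resulting birth counts towards the primary outcome are not described.

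**The plan's own figure (section 9).** For 30% against 50%, two-sided 5%, 90% power, pooled variance:

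n = [1.960 × √(2 × 0.40 × 0.60) + 1.282 × √(0.21 + 0.25)]² / 0.20² = 124 per arm, as stated.

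Dividing by 0.9 for 10% loss gives 138; the protocol rounds up to 140. The sample size is sound and does not depend on the subgroups.

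**Illustration of the bias.** The protocol gives no split by transfer stage, so these inputs are assumptions:

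- Half the women have good prognosis (live birth 45%) and half poor (15%), whichever arm they are in. Overall live birth is 0.5 × 0.45 + 0.5 × 0.15 = 30% in both arms, so the true risk ratio is 1.00.
- Standard arm: blastocyst transfer in 60% of good-prognosis and 0% of poor-prognosis women, which is 30% overall.
- All women have a transfer.

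Standard arm:

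- Blastocyst: 0.135 / 0.30 = 45.0%.
- Cleavage: (0.5 × 0.4 × 0.45 + 0.5 × 0.15) / 0.70 = 0.165 / 0.70 = 23.6%.

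Brief arm, modest shift. The nearest figure in the protocol is the risk ratio of 1.24 (95% CI 1.0 to 1.53) for good-quality embryos in section 2, borrowed here as a stand-in for a different measure. It gives 0.30 × 1.24 = 37.2%, taken as 67.2% of good-prognosis and 7.2% of poor-prognosis women.

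- Blastocyst: (0.5 × 0.672 × 0.45 + 0.5 × 0.072 × 0.15) / 0.372 = 0.1566 / 0.372 = 42.1%; RR = 0.421 / 0.450 = 0.94.
- Cleavage: (0.5 × 0.328 × 0.45 + 0.5 × 0.928 × 0.15) / 0.628 = 0.1434 / 0.628 = 22.8%; RR = 0.228 / 0.236 = 0.97.

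Brief arm, large shift, to 50% (80% of good-prognosis and 20% of poor-prognosis women).

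- Blastocyst: (0.5 × 0.8 × 0.45 + 0.5 × 0.2 × 0.15) / 0.50 = 0.195 / 0.50 = 39.0%; RR = 0.87.
- Cleavage: (0.5 × 0.2 × 0.45 + 0.5 × 0.8 × 0.15) / 0.50 = 0.105 / 0.50 = 21.0%; RR = 0.89.

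| Blastocyst transfer, standard to brief | Overall RR | RR, blastocyst | RR, cleavage |
|---|---|---|---|
| 30% to 30% | 1.00 | 1.00 | 1.00 |
| 30% to 37% | 1.00 | 0.94 | 0.97 |
| 30% to 50% | 1.00 | 0.87 | 0.89 |

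Wherever allocation shifts stage, an inert intervention looks harmful in both subgroups. The direction comes from assuming that brief incubation raises the share reaching blastocyst transfer.

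**Scale against sampling error.** In the modest case, 124 per arm gives about 37 and 46 blastocyst women. SE(log RR) = √[0.55 / (37.2 × 0.45) + 0.579 / (46.1 × 0.421)] = 0.25, so the 95% interval runs a factor of exp(1.96 × 0.25) = 1.6 each way. The bias is small beside that.

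**Power of any subgroup analysis here.** If 124 per arm split evenly, each half has 62 per arm and about 63% power for 30% against 50%. For an interaction with that effect in one half and none in the other (30% in both arms), Var(log ratio of RRs) = 0.5 / (62 × 0.5) + 3 × 0.7 / (62 × 0.3) = 0.129, SE 0.359. Then log(0.50 / 0.30) / 0.359 = 1.42, and power is about Φ(1.42 − 1.96) = 30%.

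**The case against.** Three objections carry weight.

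**Severity.** These are two secondary subgroup analyses. The primary comparison is by assigned group, the sample size rests on the overall rates, and nothing in the protocol makes a conclusion depend on a subgroup. A reader might infer that the flaw undermines the main result. It does not, and this objection stands in full.

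**Frozen cycles.** A reader might infer that frozen transfer is not part of the trial, so that the first subgroup is empty. The documents do not go that far. Section 6 leaves IVF techniques to local protocols, 6.4 does not say whether the transfer is fresh or frozen, in 6.5 the word *fresh* qualifies only the scan after a positive test, and the primary outcome in section 7 is not limited to fresh cycles. Frozen transfer is undescribed, not excluded. What remains is a population that nobody could identify from the protocol.

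**Mechanism and size.** No section says that transfer stage is chosen on embryo number or quality, and nothing links natural or hormone-replacement preparation to embryo quality. All inputs to the illustration are assumed, and the large shift is a ratio of 0.50 / 0.30 = 1.67, above the upper limit of 1.53 for good-quality embryos, although the two measures differ. Section 10 also relies on embryo quality not differing significantly. So the bias is possible, not demonstrated, and may be small. Still, an interval of 1.0 to 1.53 does not rule out an effect, and no rule fixing stage before allocation is stated. Blinding the clinicians does not remove the problem, because they may respond to embryos that allocation has already changed.

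**Conclusion.** The point holds as a secondary-analysis issue. Both pre-specified subgroups are defined after allocation, so comparisons within them lack the protection of randomisation and leave out women with no transfer or no frozen transfer, contrary to the intention-to-treat principle stated in the same section. The frozen-cycle subgroup also has no described population.

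The size depends on how far allocation shifts transfer stage, which the documents do not give. Under the assumptions shown, and with no effect on live birth, the risk ratios are about 0.94 and 0.97 for a modest shift and 0.87 and 0.89 for a large one. A reader might conclude that these subgroups must give wrong answers. The documents do not support that: with no shift this source of bias is zero, and a stage settled by a rule set before randomisation would weaken the objection to the second subgroup.

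**What to change.** 1. In section 8.1, base the pre-specified subgroups on variables fixed before allocation. Female age, infertility indication and stimulation protocol are candidates: the first two appear in the eligibility criteria (5.1), and the third precedes oocyte pick-up (6.1). The protocol does not list its baseline variables, so confirm that those chosen are recorded before the envelope is opened.
2. Test each by a treatment-by-subgroup interaction in the primary model, and label the results exploratory.
3. Report transfer stage, and any comparison by cycle type, descriptively by arm only.
4. Reconcile the frozen-cycle reference in 8.1 with sections 6.4 and 6.5, or remove it if frozen cycles are outside the trial. Which applies is for the sponsor to decide.

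The cost is a change of wording, best made before outcome data are seen, with no effect on the sample size or the primary analysis. The downside is low power for interaction tests in 280 women (about 30% in the case worked above), so few replacement subgroups should be named.

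### Section 9 applies a per-transfer live birth rate to women randomised at oocyte pick-up, so the stated 90% power is not supported for the per-woman intention-to-treat comparison

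*Protocol*

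**What the plan says.** Protocol section 9 (Sample size estimation) gives the planning rate with its denominator: "The average live birth rate in our center from 2010-2012 was 30% per transfer". It assumes a rise from 30% to 50% in the brief incubation arm and concludes: "with 90% power and a two-sided 5% level of statistical significance, we will need to recruit 124 women in each arm". The only inflation follows: "To account for 10% loss to follow up, we will recruit 140 subjects in each group or 280 subjects for the whole study".

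The unit and time of randomisation are in section 6.3: "On the day of OPU, patients will be randomized after oocyte pick up". At that point neither fertilisation nor transfer has happened. Section 8.1 sets the analysis by intention to treat: "Outcomes for participants will be analysed in the groups to which they are assigned".

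Three other places bear on the point. Section 6.4 lists failed fertilisation among the results to be recorded. Section 7 names live birth as the primary outcome but gives no denominator. Section 6.5 ties the pregnancy scan to a fresh transfer, whereas section 8.1 plans a subgroup analysis by type of frozen cycle. The protocol does not say whether frozen transfers count towards the primary outcome.

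**The concern.** A rate per transfer is conditional on reaching a transfer. The women compared in this trial enter before that is known. A woman whose oocytes do not fertilise, or who has no usable embryo, has no live birth from that retrieval but remains in the intention-to-treat denominator. She is not lost to follow-up, because her outcome is known, so the 10% allowance does not correct the rate.

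If each woman has at most one counted transfer, the per-woman rates are the per-transfer rates multiplied by the transfer share. At a fixed risk ratio the absolute difference shrinks in the same proportion, and power falls with it. At stake is the power for the trial's only primary outcome. The missing denominator in section 7 adds a second risk. An analyst who wanted to match the planning rate could analyse per transfer, which conditions on a post-randomisation event that the intervention might affect.

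**Working it through.** **Inputs from the protocol.** Control 30%, brief incubation 50% (risk ratio 0.50/0.30 = 1.67), two-sided 5%, 90% power, 10% loss, 140 per arm (all section 9).

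**Input not in the protocol.** The share f of randomised women who reach a transfer. It is an assumption here, shown over a range.

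**Step 1: the plan's own figure.** Pooled-variance formula for two proportions, with p̄ the mean of p0 and p1:

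n = [1.960 √(2p̄(1−p̄)) + 1.2816 √(p0(1−p0) + p1(1−p1))]² / (p1−p0)²

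With 0.30 and 0.50: (1.3579 + 0.8692)² / 0.04 = 124.0 per arm. This matches. Dividing by 0.9 gives 138, against 140 stated. Conversely, 140 × 0.9 = 126 evaluable per arm, with power 90.5%.

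**Step 2: rates per randomised woman.** Assume one counted transfer per woman, no live birth without a transfer, the same f in both arms and an unchanged risk ratio of 1.67. Then p0 = 0.30f and p1 = 0.50f, and

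power = Φ{[√n (p1−p0) − 1.960 √(2p̄(1−p̄))] / √(p0(1−p0) + p1(1−p1))}

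Example, f = 0.90 and n = 126: rates 0.27 and 0.45, p̄ = 0.36; (2.0205 − 1.3305)/0.6668 = 1.035; power 85.0%.

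| No transfer | Rates per woman | Power, 126 per arm | Power, 140 per arm | n per arm for 90% before loss |
|---|---|---|---|---|
| 0% | 30% v 50% | 90.5% | 93.1% | 124 |
| 5% | 28.5% v 47.5% | 87.9% | 91.0% | 136 |
| 10% | 27% v 45% | 85.0% | 88.5% | 148 |
| 20% | 24% v 40% | 78.1% | 82.2% | 177 |

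Power passes below 90% at f of about 0.99 with 126 per arm, and at about 0.93 with all 140.

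**Step 3: other effect assumptions, 126 per arm.**
- A 20-point per-woman difference kept: 91% at 10% without a transfer (27% v 47%) and 92% at 20% (24% v 44%). Power does not fall.
- Risk ratio 1.73, the ongoing-pregnancy figure cited in section 9, in place of 1.67: 92.8%, 90.5% and 84.6% at 5%, 10% and 20%.

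**Step 4: frozen transfers.** If frozen transfers from the same retrieval count, a woman may have more than one chance of live birth, and a postponed transfer is not a failure. The per-woman rate could then be 30% or higher. If the rates return to 30% and 50%, so does the power in the 0% row.

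**The case against.** The strongest reply is that the calculation is right for its inputs and that no shortfall can be shown from the document. Several parts of this stand.

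- The no-transfer share is not given, so the size of any loss is conditional. The 20% row illustrates the range and is not an estimate.
- Women without a transfer are not lost. If follow-up were complete, all 140 per arm would be analysed and about 7% without a transfer could be absorbed.
- The result depends on the effect scale, as step 3 shows.
- The frozen-cycle subgroup in section 8.1 suggests that later transfers may have been meant to count.

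None of this removes the mismatch. Complete follow-up departs from the plan's own 10% loss. With equal transfer shares, keeping 20 points per woman needs a per-transfer effect larger than the 30% to 50% that section 9 assumes. Section 10 reports no significant difference in fertilisation or embryo quality, so the protocol gives no basis for transfer shares that differ by arm. Counting frozen transfers is nowhere stated.

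A reader might infer that the trial is underpowered as a matter of fact, or that every postponed transfer is a failed outcome. The document supports neither. The first needs a transfer share that it does not give, and the second needs a rule on countable transfers that it does not contain. Nor does it say that a per-transfer analysis is intended; the stated rule is intention to treat.

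**Conclusion.** The point holds in conditional form. The planning rate and the analysis set have different denominators, nothing in the protocol reconciles them, and the 90% power is therefore unsupported for the comparison that will be made. Under the step 2 assumptions and the plan's own 10% loss, power is roughly 78% to 85% if 80% to 90% of randomised women have a transfer, and about 82% to 88.5% if all 140 per arm are analysed. The shortfall is smaller at a risk ratio of 1.73. It disappears under a constant 20-point difference, or if counted frozen transfers bring the per-woman rates back to the planning values. The arithmetic behind 124 is not in error.

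**What to change.** 1. In section 7, state that the primary denominator is all randomised women, and say which transfers from the index retrieval count: the first fresh transfer only, or frozen transfers as well. This comes first, because a rate per retrieval is undefined without it. Align section 6.5 and the frozen-cycle subgroup in section 8.1 with the choice.
2. In section 9, replace the 30% with the centre's live birth rate per oocyte retrieval on that same definition. If the centre does not hold that figure, use 30% multiplied by a stated transfer share.
3. State whether the assumed effect is a risk ratio or an absolute difference, and report the power that 280 women give over a short range of no-transfer shares, with and without the 10% loss.

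The cost is a change of wording and a look-up in the centre's records, if they hold the figure. The downside is a stated power that is probably less favourable. No extra patients are required. If the sponsor wished to keep 90% under the step 2 assumptions, 148 to 177 per arm before loss would be needed at 10% to 20% without a transfer (165 to 197 after dividing by 0.9).

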A recent meta-analysis shows [11] brief incubation of gametes was associated with significantly higher rates of clinical pregnancy (RR: 1.84, 95% CI: 1.24–2.73), ongoing pregnancy (RR: 1.73, 95% CI: 1.27–2.33) and higher rate of implantation (RR: 1.80, 95% CI: 1.43–2.26) than standard incubation. But the rates of normal fertilization (RR: 0.98, 95% CI: 0.93–1.02), good quality embryos (RR: 1.24, 95% CI: 1.0–1.53) and polyspermy (RR: 0.84, 95% CI: 0.7–1.01) were not significantly different compared with standard incubation.

In a Cochrane meta-analysis [12] eight RCTs with 733 women were included, and showed similar results. But it only reported clinical pregnancy rate and ongoing pregnancy rate which were significantly higher in brief incubation group than standard incubation. For the miscarriage rate, there were six miscarriages in one trial including 167 women. This low quality evidence suggested no significant difference in the odds of miscarriage between brief incubation and standard incubation (OR 1.98, 95% CI 0.35 to 11.09; P = 0.44). It is important to note that the live birth rate, which is the important outcome parameter, was not reported in all these studies. It is uncertain whether brief incubation improves the live birth rate compared with standard incubation.

Drawbacks inherent to the quality of these studies, such as lack of allocation concealment and no blinding, limit the quality of the available evidence.

3. Objectives:

The aim of this randomized double blinded study is to compare the live birth rate of IVF treatment following brief incubation of oocytes and sperm versus standard incubation. The hypothesis is that a brief incubation improves the live birth rate of IVF treatment.

4. Trial design:

Eligible patients will be recruited and randomized into one of the following two groups by computer-generated random numbers that will be placed in sealed envelopes:

1. Brief incubation group: oocytes will be exposed to spermatozoa for 2 hours
2. Standard incubation group: oocytes will be exposed to spermatozoa for 20 hours

5. Subject selection and exclusion

The target population for the trial will be women undergoing IVF treatment in our unit

5.1 Inclusion criteria:

- Women under 42 years of age
- Infertile for ≥ 1 year
- Indications for conventional insemination such as tubal, endometriosis, unexplained and mild male factor
- Written informed consent

5.2 Exclusion criteria:

- Women using donor eggs/donor sperm

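### With up to two embryos transferred, a working intervention should bring more twin pregnancies per woman, yet Protocol section 7 names no multiple-pregnancy or multiple-birth outcome and section 10 rules out a safety concern from laboratory rates alone.

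*Protocol*

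**What the plan says.** - **Transfer (Protocol section 6.4).** "The transfer is performed by the team clinician with a maximum of 2 embryos being replaced". This is a ceiling. The share of women who receive two embryos is not given.
- **Expected effect (section 2).** The cited meta-analysis found "higher rate of implantation (RR: 1.80, 95% CI: 1.43–2.26) than standard incubation". The same sentence reports "significantly higher rates of clinical pregnancy (RR: 1.84, 95% CI: 1.24–2.73") and "ongoing pregnancy (RR: 1.73, 95% CI: 1.27–2.33").
- **Outcomes (section 7).** The primary outcome is live birth. The secondary outcomes are miscarriage, clinical pregnancy, implantation and four laboratory rates (normal fertilisation, polyspermy, cleavage, high-quality embryos). Multiple pregnancy and multiple birth are not among them.
- **Safety (section 10).** The section notes that normal fertilisation, good-quality embryos and polyspermy did not differ significantly in earlier work, and concludes: "Thus, there should be no major safety concern in this study".
- **Data collection (section 6.5).** "These CRFs will include details on treatment received, pregnancy outcomes, complications in pregnancy, mode of delivery and birth outcomes". The number of sacs, fetuses or infants is not named as an item.

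**The concern.** Multiple pregnancy is the foreseeable harm of the benefit under test. If each embryo is more likely to implant and two may be transferred, more women should have both implant. The laboratory rates in section 10 cannot address this. The one cited result that bears on it, implantation, comes from the same meta-analysis and is not mentioned there.

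The listed outcomes do not separate the harm from the benefit. The protocol does not define live birth rate; on the usual per-woman count a twin delivery is one success. Implantation rate is also undefined; on the usual per-embryo definition twins raise it. With the outcomes as listed, the trial could report more live births and no safety concern without any pre-specified comparison of multiple pregnancy between the arms.

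**Working it through.** **The plan's own figure.** The protocol gives no twin figure. Its sample size is the only related calculation, and it reproduces. For 30% vs 50%, two-sided 5%, 90% power, pooled variance:

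n = [1.960 × √(2 × 0.4 × 0.6) + 1.282 × √(0.3 × 0.7 + 0.5 × 0.5)]² / 0.20² = (1.358 + 0.869)² / 0.04 = 124 per arm.

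Dividing by 0.9 gives 138, against 140 stated. The sample size is not in dispute.

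**Inputs for twins per woman**
- Implantation RR, rI = 1.80 (95% CI 1.43 to 2.26), section 2.
- Pregnancy RR, rP: 1.84 (clinical) or 1.73 (ongoing), section 2; or 50/30 = 1.67 (planned live birth), section 9.
- Twin share of control pregnancies, s: not in the protocol. Assumed range 10% to 40%.

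**Method A: independent implantation.** If every woman receives two embryos that implant independently with probability p, both implant with probability p². The twin ratio is rI²:
- 1.80² = 3.24
- over the implantation CI: 1.43² = 2.04 to 2.26² = 5.11

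**Method B: no independence assumed.** Let P be the proportion pregnant and T the proportion with twins. Implanted embryos per woman are P + T. With two embryos for every woman, rI = (P₁ + T₁)/(P₀ + T₀). Putting P₁ = rP × P₀ and T₀ = s × P₀ gives

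T₁/T₀ = rI + (rI − rP)/s.

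| Pregnancy RR used | s = 10% | s = 20% | s = 40% |
|---|---|---|---|
| 1.84 (clinical) | 1.40 | 1.60 | 1.70 |
| 1.73 (ongoing) | 2.50 | 2.15 | 1.98 |
| 1.67 (planned) | 3.13 | 2.47 | 2.13 |

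For example, with rP = 1.84 and s = 10%: 1.80 + (1.80 − 1.84)/0.10 = 1.40.

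**Do the two methods agree?** Only in part. Take 30% as the control chance that at least one embryo implants. Then p₀ = 1 − √0.70 = 0.163, p₁ = 1.80 × 0.163 = 0.294, and the proportion with any implantation is 1 − (1 − 0.294)² = 0.502. The implied pregnancy RR is 0.502/0.30 = 1.67, below the 1.84 that section 2 quotes.

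**Direction.** Twins per woman rise in every case above. With rP = 1.84 the ratio would fall to 1 only at s = (1.84 − 1.80)/(1.80 − 1) = 0.05, a control twin share of 5%, which is below the assumed range.

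**The case against.** **A reader might infer that the protocol's own figures predict a threefold rise in twins.** They do not. That figure is 1.80 squared. It needs independent implantation and two embryos for every woman (or the same share of double transfers in both arms), and the protocol states neither. It also sets aside the clinical pregnancy RR of 1.84. At those two point estimates, implantations per pregnancy do not rise (1.80/1.84 = 0.98).

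**Counts and shares built on that model fail for the same reason.** Under independence one gets about 4 vs 12 twin pregnancies per 140 women, and a multiple share of pregnancies going from 9% to 17%. These figures treat the 30% as an implantation probability per randomised woman. Section 9 says otherwise: "The average live birth rate in our center from 2010-2012 was 30% per transfer". Women are randomised after oocyte pick-up, before fertilisation is known, and the 140 includes a 10% allowance for loss. With the same control share (2.67/30 = 8.9%) and RR 1.84, the ratio is 1.80 − 0.04/0.089 = 1.35, or about 4 vs 5. The multiple share would then fall (1.35/1.84 = 0.73). The agreement of the independence model with the planned 50% comes from equating implantation with live birth and does not validate it.

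**A reader might also infer that twins can only appear as benefit.** That is too strong. Section 6.5 provides for collecting all pregnancy outcomes, complications and birth outcomes, so multiples could probably be recovered. What is missing is a named outcome and a pre-specified comparison by arm.

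**Section 10 can be read as concerning incubation time only.** The transfer policy is the same in both arms and clinicians are blinded, so section 10 contradicts no other passage. That is fair. Its conclusion is nevertheless worded for the whole study, and its premises do not support it.

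**The cited RRs are not predictions for this centre.** Section 2 itself notes weaknesses in the earlier trials and calls the effect on live birth uncertain. This stands, and it is why the size is given as a range.

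**Conclusion.** The point holds as a gap in the outcome list and an unsupported inference in section 10. If brief incubation works as the cited meta-analysis suggests, twin pregnancies per woman should rise by roughly 1.4- to 3.2-fold at the point estimates. The lower end uses the clinical pregnancy RR of 1.84; the upper end assumes independence. All of these figures assume the same number of embryos transferred in both arms, and Method B assumes a control twin share of 10% to 40%. The wide intervals around the cited RRs widen the range further: the implantation CI alone moves the independence figure from 2.0 to 5.1.

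The recommendation needs the expected direction, not the exact size. Whether the multiple share among pregnancies would rise is not settled, because it falls with RR 1.84 and rises with 1.73 or 1.67. The primary analysis and the sample size are unaffected. This is a low-cost improvement, and it belongs in the protocol because sections 7 and 10 are where outcomes and safety are fixed.

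**What to change.** - **Section 7.** Add multiple pregnancy rate and multiple live birth rate as safety outcomes, each per woman randomised. Report singleton live birth beside the primary live birth rate.
- **Section 6.5.** Make sure the CRF records plurality, both at the pregnancy scan already planned and at delivery.
- **Section 10.** Replace the present inference with a statement that multiple pregnancy is an expected risk if implantation improves, and that it will be compared between arms.

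Further tables, such as embryos transferred and pregnancy complications by arm, can be left to the SAP. No change to the embryo-transfer rule is proposed.

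The cost is protocol wording, a CRF check and a few extra results, with no additional patients, visits or procedures. The trial is not sized for these outcomes, so their estimates will be imprecise and should be read through their confidence intervals. The one real downside for the sponsor is that the headline benefit may look less favourable once singleton births are shown.
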